2.3.1. Risk Assessment

Potential Risk of Clinical Significance	Summary of Data/Rationale for Risk	Mitigation Strategy
Study Intervention LY3016859		
Development TE ADA.	Incidence of TE ADA was 50% after a single dose, and up to 57% after multiple doses.	Collect samples up to 20 weeks after last dose to characterize ADA profile.
IV infusion may be associated with infusion reactions and hypersensitivity reactions.	LY3016859 is a monoclonal antibody that will be administered via IV infusion. Hypersensitivity reactions and infusion reactions may occur during treatment with such agents.	Monitor infusion reactions and hypersensitivity reactions. Guidance on management of infusion and hypersensitivity reactions are in Sections 8.2.1 and 8.2.2.
Dermatological adverse reactions similar to EGFR antagonists.	One healthy participant who received a single dose of 1 mg LY3016859 experienced a rash that was considered similar to those associated with EGFR antagonists.	Collect dermatological AEs. Stop dosing for severe dermatological AEs.
Changes in eGFR in participants with CLBP.	A modest and non-statistically significant decrease in eGFR was observed in participants with DN who received LY3016859 in Part B of Study TGAB, but not in healthy participants in Study TGAA.	Exclude participants with moderate or severe renal impairment in the study. Short dosing duration. Monitor eGFR and stop dosing if necessary. CCI [REDACTED]
Fetal harm due to in utero exposure	No effects on embryo-fetal development in enhanced pilot embryo-fetal development studies in rats and rabbits. Definitive developmental and reproductive toxicity studies are not yet completed.	Do not enroll women who are pregnant or breastfeeding in studies for LY3016859.
Study Procedures		
Participant may experience increased CLBP symptoms.	Medications that relieve CLBP pain will not be allowed until Visit 801.	Rescue medication is permitted. Standard treatment of CLBP may be restarted after Visit 801 based on investigator discretion.

Abbreviations: ADA = anti-drug antibodies; AE = adverse event; CLBP = chronic low back pain; DN = diabetic nephropathy; EGFR = epidermal growth factor receptor; eGFR = estimated glomerular filtration rate; IV = intravenous; TE = treatment emergent; TGAA = Study I5V-MC-TGAA; TGAB = Study I5V-MC-TGAB.

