5.2. Exclusion Criteria

Participants are excluded from the study if any of the following criteria apply:

Medical Conditions

- [2003] Have an estimated glomerular filtration rate (eGFR) of less than 70 ml/min/1.73m² based on the Chronic Kidney Disease Epidemiology Collaboration (CKD-EPI) formula at Visit 1 or Visit 2
- [2004] Have any clinically serious or unstable cardiovascular, musculoskeletal disorder, gastrointestinal (GI), endocrinologic, hematologic, hepatic, metabolic, urologic, pulmonary, dermatologic, immunologic, or ophthalmologic disease within 3 months of Visit 3

Prior/Concomitant Therapy

- [2005] have received any antibodies against nerve growth factor (NGF), antibodies against EGFR, or EGFR tyrosine kinase inhibitors (TKI).
- [2006] have a history of allergic reactions to monoclonal antibodies, or clinically significant multiple or severe drug allergies, including but not limited to erythema multiforme major, linear immunoglobulin A dermatosis, toxic epidermal necrolysis, or exfoliative dermatitis
- [2007] have a history or presence of uncontrolled asthma, eczema, significant atopy, significant hereditary angio-edema, or common variable immune deficiency, and

Reproductive

- [2008] women who are pregnant or breastfeeding.

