8.2.3. Adverse Events of Special Interest

Dermatological adverse reactions

EGFR antibodies or EGFR-associated TKI are associated with various dermatological AEs, including acneiform rashes, xerosis, pruritis, and photosensitivity. Secondary infection can also develop.

Participants should use sun protection during the study period. Dermatological adverse reactions should be managed by the investigator according to standard of care. Discontinuation of treatment may be considered if these AEs do not respond to topical treatment, are widespread (>30% body surface area), or are severe.

If any of these AEs are reported, sites will be prompted to provide additional information.

Renal Function

Changes in eGFR were observed in participants with DN in Study TGAB (Section 2.2). Such changes were reversible and were not associated with an increase in proteinuria. Blood and urine samples will be collected to characterize the effects of LY3016859 on renal function, and eGFR will be monitored during the study.

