6.12.3. Deaths, Other Serious Adverse Events, and Other Notable Adverse Events

The general summary of adverse of events is described in the H0P-MC-CPMP SAP Version 5.

Treatment emergent adverse events of special interest will be reported separately by preferred term. These events include

- infusion site reactions (preferred MedDRA term)
- hypersensitivity and infusion-related reactions
 - Anaphylactic reaction (SMQ)
 - Anaphylactic/anaphylactoid shock conditions (SMQ)
 - Angioedema (SMQ)
 - Hypersensitivity (SMQ)
 - Infusion-related reaction (preferred MedDRA term)
- dermatological adverse events
 - Severe cutaneous adverse reactions (SMQ)
 - Drug reaction with eosinophilia and systemic symptoms syndrome (SMQ)
- abnormal renal function
 - Renal function analyses (MedDRA HLT)
 - Renal failure and impairment (MedDRA HLT)

CCI

CCI

CCI

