6.17. Totality of Evidence for Safety

The totality of evidence for safety analysis has been briefly described in the H0P-MC-CPMP SAP Version 5. The key safety events to be considered for H0P-MC-BP01 are listed below by domain:

General Adverse Event Information

- Serious adverse events related to study treatment
- Study discontinuation due to adverse event
- Treatment discontinuation due to adverse event

Cardiovascular

- QTc prolongation: > 60 msec increase
- Serious cardiac disorders adverse event

Liver function

- Hy's Law case: Serum total bilirubin ≥ 2 and ALT ≥ 3 for at least one visit during the double-blind treatment period

Metabolic function

- Serious hypoglycemia adverse event
- Treatment emergent HbA1c: Shift from low/normal at baseline to high at least once during the double-blind treatment period

Renal function

- Treatment emergent abnormal eGFR: Shifts
 - Mild at baseline to moderate/severe during the double-blind treatment period
 - Moderate at baseline to severe during the double-blind treatment period

Dermatological

- Serious or severe dermal reactions

Hypersensitivity

- Moderate to severe infusion site reactions
- Serious or severe hypersensitivity reactions

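### On the visible text, the renal key safety event in SAP 6.17 leaves out falls from normal baseline eGFR to moderate or severe, although it counts smaller falls that start from mild

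*SAP*

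**What the plan says.** SAP 6.17 introduces its list with the sentence "The key safety events to be considered for H0P-MC-BP01 are listed below by domain". In the renal domain the event is treatment-emergent abnormal eGFR, followed by two shifts: "Mild at baseline to moderate/severe during the double-blind treatment period" and "Moderate at baseline to severe during the double-blind treatment period". The list carries no redaction mark.

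On who enters the trial, Protocol 2.3.1 gives as a mitigation "Exclude participants with moderate or severe renal impairment in the study". Protocol 5.2, criterion [2003], puts this into practice by excluding those who "Have an estimated glomerular filtration rate (eGFR) of less than 70" (ml/min/1.73m²) at Visit 1 or Visit 2. It sets no upper limit.

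On the risk, Protocol 2.3.1 records "A modest and non-statistically significant decrease in eGFR was observed in participants with DN" who received the drug in Part B of Study TGAB, and says it was not seen in the healthy participants of Study TGAA. Protocol 8.2.3 lists renal function under adverse events of special interest and adds: "Such changes were reversible and were not associated with an increase in proteinuria".

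**The concern.** The two listed shifts do not match the population the protocol admits. By design, baseline eGFR should be normal or mildly reduced. The list gives one line to a moderate baseline, which should be nearly empty, and none to a normal baseline, which may hold a large part of the sample.

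The resulting count is also out of order. A participant who crosses from normal into moderate has passed through the whole mild band, so has fallen further than someone who started in that band and ended at the same value. The second is an event and the first is not.

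Change in eGFR is a named risk of the drug, and 6.17 is where the plan collects the safety events it regards as key. An understated renal count there could make the renal domain look cleaner than the data are, mainly if many participants start with normal eGFR and the fall is steep.

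**Working it through.** The plan gives no rate, threshold or power for this event, so there is no figure of its own to reproduce. The check has a logical part, which uses only the documents, and a size part, which rests on assumptions.

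**1. Coverage of shifts.** With ordered categories normal, mild, moderate and severe, five worsening shifts end in moderate or severe.

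| Shift | Counted in 6.17 | Counted after the added line |
|---|---|---|
| normal to moderate | no | yes |
| normal to severe | no | yes |
| mild to moderate | yes | yes |
| mild to severe | yes | yes |
| moderate to severe | yes | yes |

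As written, 3 of 5 count. For the baseline groups the protocol means to enrol (normal and mild), 2 of 4 count. After the added line these become 5 of 5 and 4 of 4.

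**2. Size of fall.** The bands are not visible. Assume normal ≥90, mild 60–89, moderate 30–59, severe <30. Then 75 to 59 is a fall of 75 − 59 = 16 and counts, while 95 to 59 is a fall of 95 − 59 = 36 and does not.

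**3. How many start in the normal band (assumed).** Take baseline eGFR as Normal(m, s) truncated at ≥70, with m = 85, 95 or 105 and s = 12 or 18. The share at or above 90 is P(X ≥ 90)/P(X ≥ 70).

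- m = 85: 0.378 (s = 12), 0.490 (s = 18)
- m = 95: 0.674, 0.664
- m = 105: 0.896, 0.819

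Of 150 randomized, that is 150 × 0.378 = 57 to 150 × 0.896 = 134.

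**4. How many are moderate at Visit 3 (assumed).** Take true eGFR as the same Normal distributions without truncation, and independent measurements with a coefficient of variation of 5% or 10%. Entry requires both screening values to be ≥70. The probability that the Visit 3 value is below 60 is then at most 0.59%, or 150 × 0.0059 = 0.89 participants.

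**5. Events missed, one follow-up value (assumed).** Let the fall be Normal(d, 8 or 12), independent of baseline. An event is a follow-up value below 60. It is missed if baseline is ≥90 and counted if baseline is 70–89. For baseline b, P(event) = Φ((60 − b + d)/SD), integrated over the truncated baseline distribution. Ranges over the 12 settings, per 100 participants (100 is the planned LY3016859 arm):

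| Mean fall d | Missed | Counted |
|---|---|---|
| 0 | 0.0003 to 0.08 | 0.05 to 3.5 |
| 5 | 0.003 to 0.26 | 0.2 to 7.0 |
| 10 | 0.03 to 0.76 | 0.6 to 12.5 |
| 20 | 0.7 to 4.3 | 3.2 to 29 |

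The largest miss in every row is at m = 95, s = 12, SD = 12.

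**6. Events missed, any visit.** The event in 6.17 is a shift during the double-blind period, not at one fixed visit, so step 5 understates the count. The BP01 schedule adds chemistry at Visits 4 and 6, and there are four post-baseline double-blind visits (4 to 7). Assume 2 to 4 eGFR values with a common mean fall of 10, a within-person correlation of falls of 0.3 to 0.7, and otherwise the settings of step 5. The event is now that the lowest value is below 60. The largest miss, again at m = 95, s = 12, SD = 12, is:

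| Visits | Correlation 0.7 | Correlation 0.3 |
|---|---|---|
| 2 | 1.3 per 100 | 1.5 per 100 |
| 3 | 1.7 per 100 | 2.1 per 100 |
| 4 | 2.0 per 100 | 2.7 per 100 |

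The worst case at a mean fall of 10 is therefore about 1.3 to 2.7 per 100, against at most about 0.8 with a single value.

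**The case against.** The strongest reply is that the gap depends on what mild means, and that definition is out of sight. SAP 6.12.4 is redacted, its renal analysis was updated in Version 3, and 6.17 refers to a master SAP that was not supplied. The reference list contains two eGFR-equation papers that no visible text cites, which suggests that eGFR definitions sit in the hidden part. This stands as a condition on the point. The HbA1c line in the same list weighs against it, because there the low or normal baseline group is named outright.

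The second reply is that renal safety is covered elsewhere.

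- SAP 8 plans an eGFR shift table of baseline against the minimum, maximum and last post-baseline result.
- SAP 6.12.3 reports renal adverse event terms separately.
- eGFR and the two urine ratios are exploratory endpoints.
- Within 6.17 itself, treatment discontinuation for an adverse event is a key safety event, and Protocol 2.3.1 provides for dosing to be stopped over eGFR if necessary.

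All of this limits the harm, but none of it corrects the 6.17 count. The adverse-event routes pick up a laboratory fall only if it is reported as an adverse event or leads to discontinuation for one.

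A reader might infer that the trial could miss renal harm altogether in participants with normal kidneys. The documents do not support that: the shift table would show such falls, and the earlier decrease is described as modest and reversible.

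**Conclusion.** The point holds in conditional form and is minor. On the visible text, the 6.17 renal event omits falls from normal to moderate or severe, while counting smaller falls from mild. If the redacted or master text defines mild to include normal, the count is already correct.

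The size is illustrative only: bands, baseline distribution, falls, number of visits and correlation are all assumed. At a mean fall of 10, at most about 0.8 events per 100 are missed with one follow-up value, and about 1.3 to 2.7 per 100 in the worst case with any-visit counting. A mean fall of 20 would cost more (0.7 to 4.3 per 100 even with one value), but the protocol's account of a modest decrease does not suggest a fall of that size.

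A reader might also infer that a safety decision would be wrong because of this line. No visible decision rule, threshold or test uses the renal line alone, so the documents do not support that either.

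**What to change.** Add a third shift to the renal event in SAP 6.17, from normal at baseline to moderate or severe in the double-blind period, worded in parallel with the existing two. Keep both existing lines. State that the categories are those of the eGFR shift table, with a cross-reference to where they are defined. If that definition already places normal eGFR within mild, the count needs no change and the cross-reference alone settles the matter.

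SAP 3 records that 6.17 was added in Version 2, before unblinding for the PoC lock. If PoC data have since been unblinded, report the event under both definitions and label the revised one as such.

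The cost is one line of wording and minor programming, with no new data. The same rule applies to both arms, and the event count may rise slightly in each.

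### The renal key safety event in SAP 6.17 counts two eGFR category shifts and no size of fall, so under assumed category limits most individual falls of 30% or more stay off that list

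*SAP*

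**What the plan says.** SAP 6.17 lists the key safety events for the totality-of-evidence analysis by domain. The renal entry is headed "Treatment emergent abnormal eGFR: Shifts" and has two rows: "Mild at baseline to moderate/severe during the double-blind treatment period" and "Moderate at baseline to severe during the double-blind treatment period". Neither uses a percentage or absolute change, and neither starts from a normal baseline. The visible text does not define mild, moderate or severe.

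Protocol 5.2 excludes anyone with an eGFR "of less than 70 ml/min/1.73m² based on the Chronic Kidney Disease Epidemiology Collaboration (CKD-EPI) formula at Visit 1 or Visit 2". Protocol 2.3.1 gives the intent as "Exclude participants with moderate or severe renal impairment in the study". It also gives the reason for watching eGFR: "A modest and non-statistically significant decrease in eGFR was observed in participants with DN who received LY3016859", in Part B of the earlier study and not in healthy participants.

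eGFR is covered elsewhere too. It is an exploratory endpoint (Protocol 3, SAP 4.3), and renal function is an adverse event of special interest (Protocol 8.2.3, SAP 6.12.3). SAP 8 plans, for the final lock, an eGFR shift table by minimum, maximum and last value, and laboratory change from baseline by visit. SAP 6.12.4, which holds the renal laboratory analysis, is redacted.

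**The concern.** The population is selected for good renal function, so most participants start well above the level at which a shift out of mild can happen. A rule that counts only boundary crossings then depends as much on where a person starts as on how far they fall. A small fall from just above the boundary scores, a much larger one from higher up does not, and a normal baseline never scores.

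A fall in eGFR is the renal risk that the protocol names for this antibody, and SAP 6.17 is where such events are gathered for the overall safety assessment. If large individual falls are mostly left out there, the renal line can look quieter than the data are. The same list already uses a size of change in another domain: the QTc event is an increase of more than 60 msec.

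**Working it through.** The documents give no figure for the renal event, so there is none to reproduce.

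**Inputs from the documents.** The two shift rows (SAP 6.17), the entry limit of 70 (Protocol 5.2), and four post-baseline visits in the double-blind period, Visits 4 to 7 (Protocol 1.3).

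**Assumed inputs.** Normal is 90 or more, mild 60 to below 90, moderate 30 to below 60, severe below 30. The 30% threshold is also a choice made here.

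**Step 1. Where a 30% fall stops being counted.** The baseline from which a 30% fall lands on the lower limit of mild is limit / 0.70.
- Limit 60: 60 / 0.70 = 85.7.
- Limit 70: 70 / 0.70 = 100.0, although under the written rows nothing from 90 upward is counted anyway.
- Limit 45: 45 / 0.70 = 64.3. This is below the entry limit, so an exact 30% fall from any baseline of 70 or more would be missed.

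**Step 2. The written rows applied, with limits 60 and 90.**

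| Baseline | Fall | Ends at | Shift | Counted |
|---|---|---|---|---|
| 70 | 15% | 59.5 | mild to moderate | yes |
| 86 | 30% | 60.2 | stays mild | no |
| 90 | 40% | 54.0 | normal to moderate | no |
| 90 | 70% | 27.0 | normal to severe | no |
| 100 | 30% | 70.0 | normal to mild | no |
| 129 | 30% | 90.3 | stays normal | no |

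From a mild baseline B, a fall must exceed 1 - 60/B to be counted: 14.3% from 70, 25.0% from 80, 30.2% from 86, 32.6% from 89. So between 86 and 90 a fall slightly larger than 30% is still counted. From 90 upward none is.

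**Step 3. How often this matters.** Simulation with 2,000,000 participants per scenario: true eGFR mean 85 or 98, SD 14 or 15, within-person CV 5%, 7% or 9%, two screening values of at least 70, one baseline value, and one later value after a true 30% fall. Ranges are across scenarios.
- Baseline of 85.7 or more: about 58-82% of participants.
- Baseline below 60, needed for the moderate-to-severe row: 0.4% or fewer.
- Observed falls of 30% or more that are counted as written: about 16-44%.
- The same with a normal-to-moderate/severe row added: about 22-54%.
- All participants flagged by the written rule, whatever their observed fall: about 13-39%.

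**Step 4. What a 30% flag does when the effect is small or absent.** With true ratio r of later to baseline value and within-person CV c, one sample is flagged with probability Φ(-(r - 0.70) / (c√(r² + 0.49))).
- True 10% fall (r = 0.9): c = 5% gives 0.2/0.0570 = 3.51, or 0.02%; c = 9% gives 0.2/0.1026 = 1.95, or about 2.6%. The written shift rule flags about 0.2-2.4% in the same setting.
- No effect (r = 1), c = 9%: 0.3/0.1099 = 2.73, or about 0.3% per sample and at most about 1.3% over four samples.
- A 25% threshold, no effect, c = 9%: 0.25/(0.09 × √1.5625) = 2.22, or about 1.3% per sample and at most about 5% over four.

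**The case against.** A reader might infer that a drug-related fall would leave the renal row at zero. It would not: under a true 30% fall the written rule still flags about 13-39% of participants. What is lost is individual falls, not all sign of a large group effect.

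A reader might also infer that large falls go unreported. The documents do not support that. The shift table and change-from-baseline summaries in SAP 8 would show many of them, and the redacted 6.12.4, or the master SAP that 6.17 refers to, may already hold a percentage-change analysis or the category limits.

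The earlier signal was modest, seen only in diabetic nephropathy, and described in Protocol 8.2.3 as reversible and without increased proteinuria. For an effect of about 10%, a 30% flag gains little, and at low within-person variability it flags fewer people than the present rule. A short list of abnormal values by category is also a coherent choice; the HbA1c event in the same section is a shift.

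All of this limits the weight of the point. It does not put a size-of-fall criterion into the key-event list. The visible final-lock outputs do not fill that gap: the shift table is again categorical, and box plots do not count participants. The HbA1c event does count shifts that start from normal, which the renal event does not.

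**Conclusion.** The point stands as a cheap improvement of low to moderate severity, confined to the key-event list in SAP 6.17. As written, the renal event ignores the size of the fall, cannot count anyone with a normal baseline, and spends one of its two rows on a baseline that entry all but rules out. Those facts follow from the visible text, whatever the exact limits.

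The figure of about 86 rests on an assumed mild/moderate limit of 60 (100 if the limit were 70), and the 30% is not from the documents. The estimate that 56-84% of observed falls of 30% or more go uncounted (100% less 16-44%) rests on the assumed means, SDs, CVs and a true 30% fall. Adding the normal-baseline row alone would still leave about 46-78% out. The visible text shows no decision rule tied to this row, so nothing here says that a safety conclusion would change.

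**What to change.** In SAP 6.17, renal domain, beside the existing shifts:
- Add: decrease in eGFR of at least 30% from baseline at any visit during the double-blind treatment period, by arm, with the number confirmed at the next sample. For a fall first seen at Visit 7, the chemistry sample at Visit 801 can serve.
- Add a row for normal at baseline to moderate or severe.
- Footnote the moderate-to-severe row as not expected under the entry criterion.
- State the eGFR category limits, or point to where they are defined.

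The cost is a few lines of SAP text and one derived flag from eGFR values already collected. The downside is that 30% is a reporting choice, so a 25% version should stand beside it. Neither the gain for a modest effect nor the chance rate is zero: at a within-person CV of 9%, chance alone would flag up to about 1% per arm at 30% and up to about 5% at 25% over four samples, which is why confirmation and the comparison between arms matter. This is an analysis flag only and changes no dosing or stopping rule.

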6.18. Annual Report Analyses

Analyses will be produced as needed for the purposes of providing periodic safety reviews to regulatory agencies (e.g. Development Safety Update Reports.) Data from this ISA will be combined with data from other clinical studies that investigated LY3016859. In all analyses, a combined LY arm will be created which includes participants assigned to any dose of LY3016859 in the included studies, including LY-combination regimens.

The following data will be summarized by treatment group.

- Enrollment (ongoing and completed)
- Demographics (Race, ethnicity, and gender)
- Exposure
 - Cumulative number of subjects exposed to LY3016859
 - Cumulative number of subjects exposed to LY3016859 by age
 - Cumulative number of subjects exposed to LY3016859 by sex
 - Cumulative number of subjects exposed to LY3016859 by race
- Cumulative summary of serious adverse events

The following listings will be provided.

- List of serious adverse events during the reporting period
- List of subjects who died
- Cumulative list of subjects who discontinued due to an adverse event (discontinued from treatment or study)
- List of subjects who discontinued due to an adverse event during the reporting period

Additional analyses may be added or omitted at the time of report submission as needed.

